### 1.3. Theoretical Basis for the Implementation Trial

We will assess the effectiveness of two different approaches to implementation: 1) a “standard” multifaceted implementation approach (SA) and 2) a “tailored” approach to implementation (TA). Both will be based upon a rigorous approach to designing the implementation strategies called Intervention Mapping, which is a systematic intervention development protocol that incorporates theory, evidence, and stakeholder perspectives to ensure that intervention components address key determinants of change.

Consistent with best practices in implementation science, our study is guided by theoretical frameworks to inform implementation processes (Intervention Mapping), identify implementation barriers and facilitators (Consolidated Framework for Implementation Research; CFIR), and assess implementation outcomes (Proctor et al.’s implementation outcomes framework). Intervention Mapping provides a methodological framework that will yield standard and tailored approaches to implementation. The CFIR is a comprehensive framework that identifies 39 factors that influence implementation outcomes. We will primarily focus on one of the five CFIR domains, the “inner setting,” which will drive our assessment of HIV test site contextual factors that are likely to vary across sites. These factors include the age, maturity, and size of the test site; norms of the test site; organizational readiness to change; implementation leadership; and implementation climate. We posit that tailoring implementation strategies to address test site context will improve test site context and lead to better implementation and effectiveness outcomes. Proctor et al.’s framework also guides our assessment of key implementation outcomes: fidelity, penetration, acceptability, and cost.

As depicted in the conceptual framework (**Figure 3**), the effectiveness of SNaP scale-up will be determined by the implementation processes as operationalized through the SA and TA approaches. The two implementation approaches, SA and TA, must be implemented well (e.g. with fidelity), which in turn, affects SNaP implementation. Successful implementation of SNaP, with high fidelity, penetration and acceptability will lead to better effectiveness outcomes (ART uptake).

[figure not shown]

FIGURE 3. CONCEPTUAL FRAMEWORK

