#### **4.2.2 Tailored Implementation Package:**

##### **Tailored Approach (TA): Intervention Mapping + tailoring (TA)**

In addition to having access to the standard implementation package, TA sites will have access to a broader menu consisting of 4-6 strategies identified through the Intervention Mapping process. Participating agencies (provincial health officials, HIV test sites) in TA will receive resources and coaching to assist them in tailoring their implementation strategy to address key determinants of change throughout the implementation process. Consistent with our guiding determinant framework (CFIR^9), we will assess inner setting factors that may influence implementation processes, including: organizational readiness to change, implementation leadership, and implementation climate, and available resources.

We will conduct this assessment using a structured form to be completed by each of the 21 clinics in the TA arm electronically, prior to implementation. These assessments will suggest site-specific targets for change that could be addressed through tailored implementation strategies.

Each TA site will also receive three 1-hour coaching sessions from the central TA implementation team via video-conference. These calls will address additional site-specific barriers to implementation through a structured brainstorming process,

prioritizing barriers that are most important and modifiable, and selecting theory and evidence-based strategies from the Intervention Mapping-based menu that address them. Some test sites will need to engage in strategies in addition to the standard implementation package to address site-specific needs. However, some sites may not need to use all strategies outlined in the standard IM implementation package. For example, if a test site already has strong supportive leadership in place, it may not need to use the leadership buy-in activities.

A central TA implementation team will have monthly calls with local implementation teams to monitor each TA site. Calls will focus on site-specific challenges and assess ongoing implementation. If adjustment is needed, site-specific standard operating procedures (SOP) will be updated by the site and reviewed centrally, and the central TA implementation team will re-train TA site implementation staff by video-conference.

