## 7. STUDY ASSESSMENTS AND OUTCOMES

### 7.1. Site-level Assessments

**To assess the site characteristics**, we will ask test sites (site directors and staff) to provide information at the start of the study (i.e., at baseline, pre-implementation), and at 12- and 24-months post-implementation on the following site characteristics:

Site demographic characteristics (in the past 1 month):

- a. Number of HIV tests performed
- b. PWID size (number of HIV tests performed who are PWID)
- c. PWID proportion (number of PWID over total tests performed)
- d. Sex distribution (men and women who are PWID)

Site context characteristic measures (**Table 1**):

- a. Organizational readiness to change – ORIC scale
- b. Implementation leadership – Implementation Leadership Scale
- c. Implementation climate – Implementation Climate Scale

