### **8.2.3 High and Low Performing and Sustaining Site Characterization- Analyses (Aim 3)**

**Aim 3 - Qualitative data analyses:** All qualitative interviews will be audiotaped, transcribed, translated, coded and computerized for analysis using Atlas.ti v.8 software. Analysis will begin as data are collected so that topics for further exploration can be incorporated into ongoing fieldwork. Qualitative data analysis consists of the search for patterns in data and conceptualizing ideas that help explain the presence of those patterns. Textual data analysis will involve five steps: 1) reading for content; 2) deductive and inductive coding; 3) data display to identify emerging themes; 4) data reduction; and 5) interpretation. Memos will be written for each code. Codes will be refined during the process of analysis. Responses of navigators and counselors, test site staff, and test site directors will be compared within and across the staff groups and within and across high and low performing and sustaining sites. For example, we will compare navigator and counselors' attitudes around implementing SNaP, including PWID-related stigma, competing job responsibilities at the site, perceived effectiveness of SNaP, and perceived status/value of being navigators and counselors, by high and low performing sites to understand if and how these attitudes may ultimately affect site performance.

**Aim 3 - Quantitative data analyses:** The site characteristics will be assessed with exploratory analyses to examine associations with high and low performing and sustaining clinics. Site is the unit of analysis. Given the small sample size, we will assess each site measure separately. We will use a generalized linear model with a logit link and binomial error distribution to assess the dichotomous outcome of high or low performance and sustainment. Individual implementation or demographic measures will be included as an explanatory variable, with an indicator variable for study arm, and an interaction term (assessed with  $\alpha=0.10$ ). The interaction term will aid in interpreting whether a specific characteristic modified the effect of the implementation strategy. Two sets of models will be constructed: baseline measures only and change from baseline to evaluation.

**Data triangulation:** IDI and quantitative data will be triangulated to understand SNaP

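### Aim 3 reads an arm-by-change interaction as effect modification, although change in site context occurs after randomisation and is something tailoring is meant to produce

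*Combined protocol and SAP*

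**What the plan says.** Section 8.2.3 (Aim 3, quantitative analyses) takes the site as the unit and uses a "generalized linear model with a logit link and binomial error distribution to assess the dichotomous outcome of high or low performance and sustainment". Each site measure is entered on its own, "with an indicator variable for study arm, and an interaction term" tested at alpha 0.10. One sentence gives the meaning of that term: "The interaction term will aid in interpreting whether a specific characteristic modified the effect of the implementation strategy". The next extends the scheme: "Two sets of models will be constructed: baseline measures only and change from baseline to evaluation". The change models get no separate interpretation, mediation analysis or caveat.

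Two other sections bear on what change represents. Section 1.3 states the theory of the trial: "We posit that tailoring implementation strategies to address test site context will improve test site context and lead to better implementation and effectiveness outcomes". Section 4.2.2 says of the pre-implementation assessment of readiness, leadership, climate and resources in the TA sites: "These assessments will suggest site-specific targets for change that could be addressed through tailored implementation strategies".

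On timing, Section 7.1 collects the site measures at baseline "and at 12- and 24-months post-implementation on the following site characteristics". Section 7.5 defines successful implementation at 24 months. Section 5.4.1 places the sustainment survey 6 to 10 months after SNaP activities end at a site.

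**The concern.** An interaction between randomised arm and a site characteristic describes effect modification when arm could not have influenced the characteristic. Baseline readiness, leadership and climate broadly meet that condition. Change in those scales does not. It needs a follow-up measurement taken after sites have worked under the standard approach (SA) or TA, and the protocol's own theory places improved context on the path from TA to better outcomes. Change is thus a presumed mediator. A TA site and an SA site with the same change are not like-for-like sites, so the difference between them at a given change is not a randomised contrast.

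There is also a timing problem for the performance outcome. If the evaluation is the 24-month survey, context and performance are measured together, and success could have improved the scores rather than the reverse. Section 8.2.3 does not say whether the evaluation is at 12 or 24 months. The timing point does not apply to sustainment, which is measured later; the mediator point applies to both outcomes.

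At stake is what Aim 3 may claim. A significant interaction in a change model could be reported as a finding about which sites benefit from tailoring when the model cannot show that.

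**Working it through.** The plan gives no power or error rate for the Aim 3 interaction, so there is no stated figure to reproduce. The argument is structural; the simulations only illustrate it.

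**Inputs from the documents.** Logistic model, terms and alpha 0.10: Section 8.2.3. Forty-two sites, 21 per arm: Sections 2.2 and 5.1.4. Baseline survey after randomisation but before SNaP starts: Section 5.1.5. Follow-up surveys: Section 7.1. Theory: Sections 1.3 and 4.2.2.

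**Step 1: what the interaction estimates.** With A = 1 for TA and X the site measure, the model is

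logit(p) = b0 + b1·X + b2·A + b3·X·A.

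At X = x the arm contrast is b2 + b3·x. If X is a baseline value, randomisation makes sites with the same x comparable, and b3 shows how the TA effect varies with x. If X is change, a site reaching x under TA and one reaching x under SA may differ in underlying capacity, so b2 + b3·x mixes the TA effect with that difference.

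**Step 2: a closed-form example.** All values are assumed. Let U be unmeasured site capacity, each e an independent error, and U and e have variance 1. SA change is C = e; TA change is C = 0.8 − t·U + e; the continuous outcome is F = 0.5·C + 0.7·U + e.

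- Slope of F on C in SA: 0.5.
- Slope in TA: 0.5 + 0.7·cov(U,C)/var(C) = 0.5 − 0.7t/(1 + t²).
- Interaction: −0.7t/(1 + t²).
- t = 0.3: −0.21/1.09 = −0.19. t = 0.6: −0.42/1.36 = −0.31. t = 0.9: −0.63/1.81 = −0.35.

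The outcome equation has no arm-by-change term, yet the fitted interaction is negative. This is not a pure null: the TA effect on F is 0.5(0.8 − t·U), which does vary with capacity. With the planned logistic model, 42 sites and 2,000 trials per setting, repeat runs rejected in about 10% to 19% of trials over these values of t, and in 8% at t = 0.

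**Step 3: the planned model with a constant arm effect.** In the first three rows below, the arm effect on the logit is 1.0 in every site, U has coefficient 1.0 and change has no effect on the outcome. In the fourth, TA acts only through change. Coefficients come from 400,000 simulated sites; rejection rates come from up to 2,000 trials of 42 sites (at least 1,967 usable fits).

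| Assumed mechanism | Arm, unadjusted | Arm at zero change | Arm × change | Rejection, change model | Rejection, baseline model |
|---|---|---|---|---|---|
| Arm does not affect change | 0.826 | 0.905 | −0.007 | 8.0% | 11.0% |
| TA adds 0.8 to mean change | 0.823 | 0.535 | 0.003 | 9.2% | 9.6% |
| TA lifts context whatever the capacity; SA change tracks capacity | 0.833 | 0.896 | −0.765 | 32.0% | 10.4% |
| TA acts wholly through change | 0.722 | −0.004 | 0.007 | 4.3% | 10.4% |

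Simulation standard error near the nominal level: √(0.10 × 0.90/2000) = 0.0067, about 0.7 percentage points.

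**Step 4: reading the table.** Row 3 gives a clear interaction although the arm effect is the same in every site. Rows 2 and 4 give no interaction, but the arm term moves from 0.82 to 0.54 and from 0.72 to about zero, so it no longer measures what TA achieved. The baseline model stays near its nominal level throughout (9.6% to 11.0%).

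**The case against.** The strongest reply is that the plan already limits the inference. Aim 3 is a secondary, exploratory objective, the interaction is only to help interpretation, Section 8.2.3 calls the integrated data descriptive, and results are set beside interviews. No decision rule uses the test. This stands and keeps the point minor. It does not make the reading correct: exploratory status concerns the strength of evidence, not what a coefficient means.

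A second reply is that the size is assumption-driven. That is also right. No simulation input comes from the documents, two of the four mechanisms in the table show neither an interaction nor inflated rejection, and another rejects below nominal. No rate here should be quoted as the error rate of the plan.

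Three stronger readings are tempting and unsupported:

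- A reader might infer that the change models would make TA seem to work only where climate improved. The documents give no direction, and wherever the simulations produced a distinct interaction it was negative, which would favour TA where context improved less.
- A reader might infer that the trial's randomised comparison is compromised. It is not: the intent-to-treat analysis in Section 8.2.1 does not use change scores. Only the arm term inside the change models is affected.
- A reader might infer that these models will decide where TA is deployed. Section 8.2.3 speaks of informing other settings that implement SNaP, and Section 1.2 lists site characteristics beside effectiveness and cost.

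Finally, within-arm associations use the same two slopes as the interaction model, so much of the remedy is a matter of test and wording. That is true, but the wording carries the error.

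**Conclusion.** The point holds as a minor one. For the three context scales, the stated interpretation of the interaction is valid for baseline values and wrong for change from baseline, and nothing elsewhere in the document corrects it. The conclusion rests on the protocol's own premise that tailoring alters context, not on any simulated figure. Depending on mechanism, rejection under the planned model ranged from 4.3% to 32% against a nominal 10%; this shows that the problem can matter, not how large it will be.

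Two limits apply. The mediator argument is made for the context scales; the theory posits a TA effect less clearly for change in site demographics such as test volume, although those changes too are observed after randomisation. And baseline values are sound moderators only if the survey precedes knowledge of allocation. Section 5.1.5 places it after randomisation and before implementation, and Section 5.1.6 times SNaP training, but not the survey, against notification of arm.

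**What to change.** In Section 8.2.3:

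- Limit the interaction test and the effect-modification sentence to baseline measures.
- For change in readiness, leadership and climate, report the association with performance or sustainment within each arm, labelled descriptive, and say that it is not the effect of TA or a modifier of it.
- Analyse each 24-month context scale as an outcome by arm, adjusted for its baseline value. This directly tests the Section 1.3 premise that tailoring improves context.
- State whether the evaluation used for change is the 12- or 24-month survey.

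The cost is SAP wording and a few simple added models. All the data are already scheduled, and no primary analysis changes.

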### 8.3. Potential Biases and Solutions

Potential biases of this study, among both PWID and Site Directors/Site Staff participants, include selection bias during recruitment and social desirability bias during the assessments.

#### *Social Desirability Bias*

Some questions asked to the PWID subsample cohort may be sensitive. For example, we may ask about participants’ drug use, injection drug use, alcohol use, sexual behaviors, HIV testing history, HIV care seeking behaviors and ART adherence. Participants may provide answers they perceive the interviewers want to hear. Social desirability bias may also occur among the Site Directors and Site Staff, as they may feel pressure to show their clinic and/or staff in a positive light.

Efforts to prevent social desirability bias and encourage accurate responses among participants include emphasizing confidentiality of all participant responses, and assuring participants that their responses and participation in the study will have no effect on the quality of their health care or access to health care (for PWID) and no effect on employment status or treatment in the workplace (for Site Directors and Staff). Also, interviewers and study staff will be trained to maintain strict confidentiality, to build rapport with participants and to ask questions in a respectful and non-judgmental way. Additionally, for Site Directors and Staff, we will ensure that their responses will not be shown to any other staff or supervisors at the clinics.

#### *Selection Bias*

Participation in the study is completely voluntary, and it is possible that those who agree and consent to participate in the study may have different characteristics from those who do not participate. In turn, difference in characteristics may be associated with differences in study results. We will minimize selection bias by assuring confidentiality to all potential participants and addressing any concerns that may arise among potential participants who are hesitant to join the study. We will also track the numbers who decline to participate in the study, providing an estimate of the extent of potential selection bias that may exist.

## 9. HUMAN SUBJECTS CONSIDERATIONS

### 9.1. Ethical Review

This protocol, the template informed consent form, participant education and recruitment materials, and other requested documents — and any subsequent modifications — will be reviewed and approved by the ethical review bodies responsible for oversight of research conducted at the study site.

Subsequent to initial review and approval, the responsible IRBs/ECs will review the protocol at least annually. The Investigators will make safety and progress reports to the IRBs/ECs at least annually, and within three months of study termination or completion. These reports will include the total number of participants enrolled in the study, the number of participants who completed the study, all changes in the research activity, and all unanticipated problems involving risks to human subjects or others. The Principal Investigators and UNC Project Vietnam are responsible for the submission of continuing review to the required ethical review bodies.

### 9.2. Informed Consent

Electronic voluntary informed consent will be obtained from each study participant. Participants who consent to participation in the study will provide electronic signatures via tablets or laptops. The study site is responsible for developing study informed consent forms for local use that describes the purpose of the study, the procedures to be followed, and the risks and benefits of participation, in accordance with all applicable regulations. The study site also is responsible for translating the template form into the local Vietnamese language, and verifying the accuracy of the translation by performing an independent back-translation.

Literate participants will document their provision of informed consent by signing their electronic informed consent forms. Non-literate participants will be asked to document their informed consent by marking their informed consent forms (e.g., with an X, thumbprint, or other mark) in the presence of a literate third party witness. Participant literacy will be determined according to local site SOPs. Any other local IRB/EC requirements for obtaining informed consent from non-literate persons also will be followed.

Participants will be provided with a copy of their informed consent forms if they are willing to receive them.

**PWID participants:** All PWID participants who are confirmed HIV-infected (n=6200) will be given a brief consent form during post- test counseling. This consent will address permission to: 1) extract ART uptake from medical records at local ART clinics and 2) extract MAT uptake from medical records at MAT clinics. Note that consent for SNaP will not be explicitly requested, as SNaP will be incorporated as a routine clinical activity. However, audio-recording of post-test counseling for purposes of fidelity measuring is not part of routine clinical activity, therefore we will obtain consent for all audio-recording the post-test counseling.

The PWID subsample cohort (n=1500) will have *an additional consent* to allow re-contact at a later date and to obtain locator information, including information of a family member.

**Site directors and site staff participants:** HIV test site directors and staff will provide electronic informed consent prior to quantitative and qualitative interviews.

### 9.3. Risks

This study does not introduce new drugs, new therapies, or new indications for existing drugs, but rather aims to understand ways to best implement the SNaP intervention to increase ART and MAT uptake, and suppress viral load.

Our study will not increase the risk of participants who present to HIV test sites. In Vietnam, it is illegal to share medical records outside the health system and this is clearly understood by all practitioners including those that provide HIV and MAT (specifically, methadone in Vietnam) related care. Based on our qualitative research with providers and law enforcement officers for HPTN 074, as well as more than a decade of experience conducting HIV studies in Vietnam, disclosure of ARV and MAT patients to law enforcement officials does not occur. Furthermore, methadone maintenance treatment (MMT) guidelines and DECREE 96/2012/NĐ-CP state that MMT patients are exempt from mandatory detoxification centers, even if MMT participation is suboptimal.

There may be some discomfort to directors and staff working in HIV test sites identified as low-performing/low-sustaining. However, we will work closely with the Vietnam Administration for HIV/AIDS Control (VAAC) to minimize this risk and minimize any risk that authorities will treat sites or staff differently based on performance identified by our study. In a pilot ART/MMT integration study among 18 clinics and 3 provinces conducted by VAAC in 2012, there were instances in which clinic staff and local leaders resisted ART/MMT integration and were not able to successfully integrate service. No punitive measures were taken against these clinics or their leaders or staff. Furthermore, during formative research our team has conducted on ART/MMT integration, clinic staff, local leaders, and VAAC representatives openly discussed barriers to integration and identified productive approaches that could be employed to overcome the difficulties that both leaders and staff may encounter.

Similarly, we do not anticipate any punitive measures to HIV test sites that are less successful in SNaP implementation or sustainment. We have worked closely with the VAAC and the National AIDS Committee for over 15 years on several sensitive projects. The VAAC is engaged and committed to providing technical support for the scale-up of SNaP in Vietnam and strongly supports this proposed research.

There will be no additional risks or side effects for participants presenting to SA sites compared to participants who presenting to TA sites.

Dried blood spots will be collected from PWID who consented to participating in the subsample cohort. Dried blood spot collection consists of a finger prick to the participant. There are minimal risks to dried blood spots, such as a slight pain when the finger is pricked. To reduce the possibility of pain, dried blood spot collection will be taken by trained staff. Participants may decline the dried blood spot collection with no consequence to their care. Participants may return for their results, and trained staff will provide results referrals to appropriate health care services as requested or necessary.

A small risk of psychological distress is posed by study questions such as those concerning HIV risk, drug use, and disclosure of HIV serostatus. Participants may find answering questions

about these issues upsetting: these questions will be asked in as sensitive a manner as possible, and participants may decline to answer at any time. If a participant experiences emotional upset during the interview, the research staff will be trained on how to handle these situations and the principal investigators will be available to speak with participants if needed.

Specific and appropriate protocols will be in place to ensure a participant's safety should a research staff member feel that a participant is in danger of harming himself or others during the course of a study visit. We will also remind participants that they can terminate the interview at any time.

Although study sites will make every effort to protect participant privacy and confidentiality, it is possible that participants' involvement in the study could become known to others, and that social harms may result (i.e., because participants could become known as HIV-infected). For example, participants could be treated unfairly or discriminated against, or could have problems being accepted by their families and/or communities."

Study-related visits will not be conducted in prisons or jails with study participants. Incarcerated participants will be eligible to resume study participation upon release.

*Steps taken to ensure that potential participants do not feel coerced to enter or remain in the study:* Research staff recruiting participants will follow a standardized script to ensure that all ethical issues are adhered to and that study protocols are followed. For PWID participants, all written and oral communications about the study will emphasize that this study is completely voluntary and will not impact employment status, or the entitlement for the MAT or HIV services, hospital or other clinics or testing sites, and that they can drop out of the research at any time without jeopardizing their entitlement to any of these services. For HIV test site directors and staff participants, all written and oral communications about the study will emphasize that this study is completely voluntary and will not impact employment status, and that they can drop out of the research at any time without jeopardizing their jobs. In addition, interviewers reviewing consent with participants will be trained to probe for comprehension.

